### **Secondary Objectives:**

To investigate the following in patients after nerve sparing prostatectomy treated with MED3000 for 12 weeks:

1. The efficacy of MED3000 in patients at weeks 4, 8 and 12 using:
  - a. The change from baseline in Self-Esteem and Relationship (SEAR) questionnaire for men
  - b. The change from baseline in Urinary incontinence using the Expanded Prostate Cancer Index Composite (EPIC) - (climacturia question added to EPIC)
  - c. Change from baseline in all domains of the IIEF.
2. The change from baseline in 24 hour pad weight and usage number per day at 12 weeks.
3. The change from baseline of the stretched flaccid penile length following 12-weeks of treatment
4. Treatment-related adverse events in male patients and female partners occurring during treatment with MED3000.

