***Female partner exclusion criteria***

- 1. Unwillingness of the partner to make the required attempts at sexual intercourse during the screening period (4 requested sexual intercourse attempts) and during the 4-weekly assessment periods (4 requested sexual intercourse attempts per period) in the treatment phase.
- 2. Unwilling to disclose any experienced adverse events to the site study team.
- 3. Partner cannot communicate reliably with the Investigator
- 4. Any other condition that would prevent the patient from completing the study, as judged by the Investigator

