### **Adverse Events**

AEs will be monitored and assessed throughout a patient's involvement in the study (from the point of signing the ICF to the follow up visit (Visit 6). At each study visit, the site staff will ask the patient about any AEs the patient and their partner may have experienced. The site study staff will also ask the patient about any device deficiencies that they experienced.

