### **9. Statistical Analysis**

#### ***Sample size calculation***

It is planned to enrol and treat approximately 20 patients for a 12-week treatment duration. There is no formal sample size calculation performed. This is an exploratory study for treatment of novel patient population without precedent.

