### ***Statistical analysis***

Baseline characteristics of the trial participants will be summarized using the following baseline data. Mean, median, minimum, maximum and standard deviation or proportion (as appropriate) will be reported.

- Age
- Baseline comorbidities
- BMI
- Baseline IIEF/ SEAR/EPIC (+climacturia question) (following 4 week screening period)
- 24 hour pad weight
- 24 hour pad number usage
- Stretched penile length
- Prostate cancer stage (surgically-verified)

Full Analysis Set: Patients who received at least one dose MED3000 topical gel treatment.

Per-protocol Analysis Set: Patients who meet the inclusion/exclusion criteria and who have completed all the treatment and follow-up sessions up to the 12-week visit.

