### **Analysis of Secondary and Safety Endpoints**

The secondary assessments are:

- Mean change from baseline in all domains of the IIEF at 4, 8 and 12 weeks, besides the IIEF-EF at 12 weeks.
- Mean change from baseline in SEAR, EPIC at 4, 8 and 12 weeks
- Mean change from baseline in stretched flaccid penile length at 12 weeks
- Proportion of patients on penile injection therapy or penile implant at 12 months follow-up
- Mean change in 24 hour pad weight and 24 hour pad number usage at 12 weeks
- Serum PSA indicative of biochemical recurrence
- Proportion of patients who experienced treatment-related adverse events

Continuous variables: Estimates of mean changes from baseline, along with 95% confidence intervals, will be produced. The change from baseline in endpoints within the group will be analysed by one-sample t-tests with a two-sided significance threshold of  $p=0.05$ , testing the null hypotheses of mean change from baseline equal to zero. Covariates / sub-groups may also be evaluated such as age and comorbidities.

Discrete variables: Estimates of proportions, along with 95% confidence intervals, will be produced.

Any missing, impossible (inconsistent with human life) or inconsistent recordings in the Case Report Forms will be referred back to the Principal Investigator and documented for each individual patient before clean file status is declared. Missing data will not be imputed.

Data will be analyzed with Microsoft Excel, Graphpad Prism 7, or equivalent statistics software. Efficacy endpoints will be analysed after the last patient has completed all follow up visits.

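### Secondary objective 4 includes adverse events in female partners, but Section 9 pre-specifies no partner summary, and the only scheduled enquiry about her events after Visit 1 goes through the man

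*Combined protocol and SAP*

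**What the plan says.** Section 2, Secondary Objectives, item 4, names both members of the couple: "Treatment-related adverse events in male patients and female partners occurring during treatment with MED3000".

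Section 9, Analysis of Secondary and Safety Endpoints, lists one adverse-event measure: "Proportion of patients who experienced treatment-related adverse events". For discrete variables it adds "Estimates of proportions, along with 95% confidence intervals, will be produced", without naming an interval method. Under Statistical analysis the main population is "Full Analysis Set: Patients who received at least one dose MED3000 topical gel treatment", and the per-protocol set is likewise made up of patients.

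On collection, Section 6 (Adverse Events) states that at each visit "the site staff will ask the patient about any AEs the patient and their partner may have experienced". The Visit 3 and Visit 4 descriptions also put the question about partner events to the man. The text under Unanticipated Serious Adverse Device Effect has adverse events written in the patient's diary and then entered in the eCRF.

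Two places look to the partner herself. Female partner exclusion criterion 2 (Section 4) rules out a woman who is "Unwilling to disclose any experienced adverse events to the site study team". Assessment of Safety (Section 6) says the investigator will monitor both the subject and the partner.

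On size: "It is planned to enrol and treat approximately 20 patients for a 12-week treatment duration", and "There is no formal sample size calculation performed".

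**The concern.** Partners are participants here. They sign their own consent form, have their own eligibility criteria, are exposed through intercourse soon after the gel is applied, and may apply it themselves. The protocol made their safety part of an objective. An analyst who follows Section 9 literally would produce a result for the men and none for the women, and any later partner table would be put together without a pre-specified definition or denominator.

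Collection raises a second, linked question. If her events are learned by asking him, some may not be passed on. With about 20 couples the expected number of affected partners is small, so one missed woman could turn a report of some events into a report of none.

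**Working it through.** **Step 1: objective against analysis.**

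| Element | Men | Female partners |
|---|---|---|
| Objective (Section 2, item 4) | Named | Named |
| Adverse-event endpoint (Section 9) | Proportion of patients | None |
| Analysis set (Section 9) | Full Analysis and Per-protocol | None |
| Event recording (Section 6) | Yes | Yes |

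Reading patients in Section 9 to include partners does not work. The protocol names the two separately in the objective, the consent text, the visit descriptions and the adverse-event text, and both analysis sets are defined by receiving or completing treatment.

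**Step 2: how partner events reach the site after Visit 1.**

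- Visits 3 and 4 (telephone): the man is asked about both.
- Visits 5 and 6: the visit descriptions cover adverse events without mentioning the partner. The general rule in Adverse Events applies, and it also addresses the man.
- Diary: the patient's. No partner diary is described.
- Visit 2 training: the partner attends only if present.
- Assessment of Safety: states the intention to monitor the partner, but the mechanisms it names are interviews with each subject and a telephone number for all subjects, after it has worded subject and partner separately.

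No visit, call, diary or questionnaire is set at which she is asked.

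**Step 3: precision of a partner proportion.** The plan states no figure for partner events, so there is nothing to reproduce. The one input from the documents is about 20 treated men, hence about 20 partners. Exact (Clopper-Pearson) 95% intervals:

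- 0/20: upper limit = 1 − 0.025^(1/20) = 16.8%, so 0 to 16.8%
- 1/20: 0.1% to 24.9%
- 2/20: 1.2% to 31.7%

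**Step 4: effect of incomplete relay (illustration only).** Let p be the true share of partners with an event and s the chance that an affected partner is recorded. Both are assumptions; the documents give neither. With independent couples, the chance of recording at least one affected partner is 1 − (1 − p·s)^20.

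| p | s = 100% | s = 80% | s = 50% |
|---|---|---|---|
| 10% | 1 − 0.90^20 = 88% | 1 − 0.92^20 = 81% | 1 − 0.95^20 = 64% |
| 5% | 1 − 0.95^20 = 64% | 1 − 0.96^20 = 56% | 1 − 0.975^20 = 40% |

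The table shows the direction and a plausible range of the effect. It does not estimate how much would be missed.

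**The case against.** The strongest reply is that the data will exist. Adverse-event recording starts once both partners have signed consent (Schedule of Assessments, footnote 6). Staff prompt for partner events, all events go into the eCRF, and one of the two serious-event definitions expressly includes the partner. Each man enrols with one consenting partner, so a denominator follows directly from the Full Analysis Set. This stands. A reader might infer that partner safety cannot be answered at all, and the documents do not support that: what is missing is a pre-specified summary, and it can be recovered from recorded data.

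A reader might also infer that her events reach staff only through him. That goes too far. The exclusion criteria require a partner who is willing to disclose events and able to communicate reliably with the investigator, she consents in person, and the investigator is to monitor her. What can be said is narrower: no scheduled step after Visit 1 puts the question to her.

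A third tempting reading is that the collected data are biased towards no events. Under-reporting by proxy is plausible, but nothing in the documents demonstrates it, and staff ask explicitly about her. Section 7 lists only penile pain or discomfort and headache as anticipated effects of the gel, so no particular partner symptom can be assumed. The capture share in the illustration applies to an affected partner, not to each event; a woman with repeated events would be missed less often than a woman with one.

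Finally, this is an exploratory study with no sample-size calculation. That limits what a partner estimate can show, but it does not explain why a stated objective has no summary when a descriptive proportion is all that is needed.

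**Conclusion.** The point holds in this form: item 4 of the secondary objectives includes female partners, and Section 9 pre-specifies no summary for them although their events are recorded. This rests on the text alone and needs no assumption.

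The described procedures also leave a risk of under-ascertainment, because the scheduled questions go to the man while other passages expect disclosure by the woman. Its size cannot be derived from the documents; the percentages in Step 4 depend on assumed event rates and capture shares and should not be read as findings.

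The primary efficacy result is unaffected. A partner proportion from about 20 couples would be descriptive: no affected partner among 20 is compatible with a true rate of up to 16.8%, and that limit is valid only if ascertainment is complete.

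**What to change.** In Section 9, add the number and proportion of female partners with at least one treatment-related adverse event. Take as denominator the partners of men who used at least one dose. Give an exact 95% confidence interval and a listing of partner events, report them separately from the men, and label them descriptive. Naming the exact method matters because Section 9 does not specify one, and a simple normal-approximation interval has zero width at 0/20.

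In Section 6, have staff ask the partner directly about adverse events at the existing Visit 3, 4 and 6 calls and at or around Visit 5. Keep the man's report as the fallback when she cannot be reached, and record which source was used. This would put into practice what the partner exclusion criterion and Assessment of Safety already intend.

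The Section 9 change costs a few lines of text. The Section 6 change needs a protocol amendment with IRB approval, and because the existing calls are to the man, occasional extra attempts to reach the partner. Neither needs more visits or a larger sample.

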## **10. Monitoring and Quality Assurance**

The principal investigator will provide monthly status updates to FMD in regard to any unanticipated AEs, SAEs etc. in addition to standard reporting of such events to IRB.

### **Withdrawal Criteria**

- Occurrence of a serious adverse event during the treatment period will result in termination of MED3000 topical gel treatment.
- A subject may be withdrawn from MED3000 topical gel treatment by the investigator, regardless of consent, if the investigator determines health and/or safety concerns preclude continuation of investigational product treatment. If a subjective is not sufficiently cooperative may be grounds for dismissal from trial participation.
- A subject may be withdrawn from the study by the investigator in the event that a late inclusion/exclusion criteria violation is found to have occurred and there are corresponding health and/or safety concerns.
- Tumor recurrence (defined as biochemical recurrence: serum PSA  $\geq 0.2$  ng/ml) during the MED3000 treatment period will result in immediate withdrawal from the study such that adjuvant/salvage therapies for cancer control will be needed.
- A subject may withdraw from the study at any time, for personal reasons or otherwise.

Information regarding the timing and type of withdrawal (treatment and/or study) will be documented. Information collected for study purposes may be maintained and used by investigators after study withdrawal has occurred, but no new information will be collected after that time. Subject withdrawal due to an AE will be distinguished from withdrawal due to other reasons by appropriate documentation.

### ***Stopping / discontinuation rules***

Completion of trial is defined as the point at which the last patient enrolled in the study has completed the visit 6 (week 13) follow-up phone call visit or withdrawn from the study.

Although unlikely to occur, the study may also be terminated early if recurrent serious protocol deviations are reported, and/or the study team is unable to continue (e.g. manpower or financial issues). In this case, a report will be filed with the IRB within 1 month, and all treated patients

will continue to be followed up until follow-up visit (Visit 6) if possible and undertake the assessments scheduled for each visit.

The final clinical study report will document the reasons for trial discontinuation if it occurs.

***Deviations from the Protocol***

Emergencies excepting, under no circumstances will prospective deviations (waivers) from the approved Clinical Investigation Plan and subsequent amendments be permitted. Any changes to the approved protocol should be covered by an amendment which will be approved by the necessary Regulatory Authorities and/or IRB as necessary.

All deviations that are identified during the course of the study, be they major or minor in severity, will be recorded on a protocol deviations tracking log. This log will be reviewed by the site staff periodically for risk and trend evaluation purposes, and corrective and preventative actions taken as necessary. Futura will be notified of all protocol deviations as part of the PI's periodic update reports.

***Monitoring, quality control and assurance***

The study coordinator or designee is responsible for quality control of the data.

The manufacturer (Futura Medical Developments Ltd) or appointed party has the option to monitor the data and perform onsite monitoring visits to ensure the precision, quality, and integrity of the data collected. The investigator(s) agrees to permit access to study records, source data, and source documents for this purpose

## **11. Privacy and Confidentiality**

- Study procedures will be conducted in a private setting
- Only data and/or specimens necessary for the conduct of the study will be collected
- Data collected (paper and/or electronic) will be maintained in a secure location with appropriate protections such as password protection, encryption, physical security measures (locked files/areas)
- Specimens collected will be maintained in a secure location with appropriate protections (e.g. locked storage spaces, laboratory areas)
- Data and specimens will only be shared with individuals who are members of the IRB-approved research team or approved for sharing as described in this IRB protocol
- Data and/or specimens requiring transportation from one location or electronic space to another will be transported only in a secure manner (e.g. encrypted files, password protection, using chain-of-custody procedures, etc.)
- All electronic communication with participants will comply with Mass General Brigham secure communication policies
- Identifiers will be coded or removed as soon as feasible and access to files linking identifiers with coded data or specimens will be limited to the minimal necessary members of the research team required to conduct the research

Mass General Brigham Institutional Review Board  
Intervention/Interaction Detailed Protocol

---

- All staff are trained on and will follow the Mass General Brigham policies and procedures for maintaining appropriate confidentiality of research data and specimens
- The PI will ensure that all staff implement and follow any Research Information Service Office (RISO) requirements for this research
- Additional privacy and/or confidentiality protections

Each enrolled subject will have a study ID substituted for names and MRNs and no identifiers will be included on their paperwork or electronic study record. All electronic data will be stored on Partners built computers updated with the latest anti-virus software and stored in locked offices on the BWH campus.

## APPENDICES

### APPENDIX 1

#### INTERNATIONAL INDEX OF ERECTILE FUNCTION (IIEF)

##### Subject Questionnaire

These questions ask about the effects that your erection problems have had on your sex life over the last four weeks. Please try to answer the questions as honestly and as clearly as you are able. In answering the questions, the following definitions apply:

- sexual activity includes intercourse, caressing, foreplay & masturbation
- sexual intercourse is defined as sexual penetration of your partner
- sexual stimulation includes situation such as foreplay, erotic pictures etc.
- ejaculation is the ejection of semen from the penis (or the feeling of this)
- orgasm is the fulfilment or climax following sexual stimulation or intercourse

Over the past 4 weeks:

*Please check one box only*

Q1 How often were you able to get an erection during sexual activity?  
0 No sexual activity  
1 Almost never or never  
2 A few times (less than half the time)  
3 Sometimes (about half the time)  
4 Most times (more than half the time)  
5 Almost always or always

Q2 When you had erections with sexual stimulation, how often were your erections hard enough for penetration?  
0 No sexual activity  
1 Almost never or never  
2 A few times (less than half the time)  
3 Sometimes (about half the time)  
4 Most times (more than half the time)  
5 Almost always or always

Q3 When you attempted intercourse, how often were you able to penetrate (enter) your partner?  
0 Did not attempt intercourse  
1 Almost never or never  
2 A few times (less than half the time)  
3 Sometimes (about half the time)  
4 Most times (more than half the time)  
5 Almost always or always

Q4 During sexual intercourse, how often were you able to maintain your erection after you had penetrated (entered) your partner?  
0 Did not attempt intercourse  
1 Almost never or never  
2 A few times (less than half the time)  
3 Sometimes (about half the time)  
4 Most times (more than half the time)  
5 Almost always or always

Q5 During sexual intercourse, how difficult was it to maintain your erection to completion of intercourse?  
0 Did not attempt intercourse  
1 Extremely difficult  
2 Very difficult  
3 Difficult  
4 Slightly difficult  
5 Not difficult

Mass General Brigham Institutional Review Board  
Intervention/Interaction Detailed Protocol

---

Q6 How many times have you attempted sexual intercourse?  
0 No attempts  
1 One to two attempts  
2 Three to four attempts  
3 Five to six attempts  
4 Seven to ten attempts  
5 Eleven or more attempts

Q7 When you attempted sexual intercourse, how often was it satisfactory for you?  
0 Did not attempt intercourse  
1 Almost never or never  
2 A few times (less than half the time)  
3 Sometimes (about half the time)  
4 Most times (more than half the time)  
5 Almost always or always

Q8 How much have you enjoyed sexual intercourse?  
0 No intercourse  
1 No enjoyment at all  
2 Not very enjoyable  
3 Fairly enjoyable  
4 Highly enjoyable  
5 Very highly enjoyable

Q9 When you had sexual stimulation or intercourse, how often did you ejaculate?  
0 No sexual stimulation or intercourse  
1 Almost never or never  
2 A few times (less than half the time)  
3 Sometimes (about half the time)  
4 Most times (more than half the time)  
5 Almost always or always

Q10 When you had sexual stimulation or intercourse, how often did you have the feeling of orgasm or climax?  
1 Almost never or never  
2 A few times (less than half the time)  
3 Sometimes (about half the time)  
4 Most times (more than half the time)  
5 Almost always or always

Q11 How often have you felt sexual desire?  
1 Almost never or never  
2 A few times (less than half the time)  
3 Sometimes (about half the time)  
4 Most times (more than half the time)  
5 Almost always or always

Q12 How would you rate your level of sexual desire?  
1 Very low or none at all  
2 Low  
3 Moderate  
4 High  
5 Very high

Q13 How satisfied have you been with your overall sex life?  
1 Very dissatisfied  
2 Moderately dissatisfied  
3 Equally satisfied & dissatisfied  
4 Moderately satisfied  
5 Very satisfied

Q14 How satisfied have you been with your sexual relationship with your partner?  
1 Very dissatisfied  
2 Moderately dissatisfied  
3 Equally satisfied & dissatisfied  
4 Moderately satisfied  
5 Very satisfied

Q15 How do you rate your confidence that you could get and keep an erection?  
1 Very low  
2 Low  
3 Moderate  
4 High  
5 Very high

Mass General Brigham Institutional Review Board  
Intervention/Interaction Detailed Protocol

---

**APPENDIX 2**

**Self-Esteem And Relationship (SEAR) Questionnaire**

**INSTRUCTIONS:** Please think about the past 4 weeks when responding to the following statements.

---

Please check  one box for each statement.

---

1. I felt relaxed about initiating sex with my partner.

- Almost always/always
- Most times (much more than half the time)
- Sometimes (about half the time)
- A few times (much less than half the time)
- Almost never/never

---

2. I felt confident that during sex my erection would last long enough.

- Almost always/always
- Most times (much more than half the time)
- Sometimes (about half the time)
- A few times (much less than half the time)
- Almost never/never

---

3. I was satisfied with my sexual performance.

- Almost always/always
- Most times (much more than half the time)
- Sometimes (about half the time)
- A few times (much less than half the time)
- Almost never/never

---

Self-Esteem and Relationship Questionnaire  
Version 2: 20FEB02 PPG Mens/Womens Health Team

Mass General Brigham Institutional Review Board  
Intervention/Interaction Detailed Protocol

---

